**LENS-Q**  
**Non-Occupational/Recreation**

\_\_\_\_\_ / \_\_\_\_\_ / \_\_\_\_\_  
Month/Day/Year

Please answer each question by circling or marking the answer as indicated. If you are unsure about how to answer a question, please give the best answer you can.

Non-Occupational/ Recreation Noise (Continued)		For each activity you answer "Yes" please answer questions 2 - 5.	4. How often were you around loud noise?	5. How often did you use hearing protection while in loud noise?
1. Have you been exposed to noise during any of these non-job related activities? (Circle No or Yes)	2. Age first started			
			Never	Never
			Several times a year	Some of the time
			Several times a month	Most of the time
			Several times a week	Always
			Daily	
RECREATION				
Have you ever attended a Professional or College:				
A. Basketball game.....	No	Yes		
B. Football game.....	No	Yes		
C. Hockey game.....	No	Yes		
D. Baseball game.....	No	Yes		
Have you ever attended an:				
E. Aerobic exercise class.....	No	Yes		
F. Car race.....	No	Yes		
G. Monster truck show.....	No	Yes		
H. Demolition derby.....	No	Yes		
I. Fireworks show.....	No	Yes		

--	--	--

Subject ID

Do not fill in - for office use only

## LENS-Q

□ / □ / □  
Month/Day/Year

### Non-Occupational/Recreation

Please answer each question by circling or marking the answer as indicated. If you are unsure about how to answer a question, please give the best answer you can.

Non-Occupational/ Recreation Noise (Continued)	For each activity you answer "Yes" please answer additional questions 2 - 5.			4. How often were you around loud noise?	5. How often did you use hearing protection while in loud noise?
	2. Age first started	3. Approximate duration (#yrs/mos)	Never		
1. Have you been exposed to noise during any of these non-job related activities? (Circle No or Yes)		Several times a year	Several times a month	Several times a week	Never
		Daily			Some of the time
					Most of the time
					Always
YARD AND GARDEN					
Have you ever used a:					
A. Chain saw.....	No	Yes			
B. Tractor.....	No	Yes			
C. Lawn mower, gas powered..	No	Yes			
D. Edger/trimmer.....	No	Yes			
E. Leaf blower.....	No	Yes			
F. Weed whacker.....	No	Yes			
G. Snow blower.....	No	Yes			
Other Non-Occupational Noise:					
H. _____					
I. _____					

Subject ID			
Do not fill in - for office use only			

**LENS-Q**  
**Non-Occupational/Recreation**

  /  /     
Month/Day/Year

Please answer each question by circling or marking the answer as indicated. If you are unsure about how to answer a question, please give the best answer you can.

6. Have you ever undergone any non-occupational accidental exposure to sudden, intense noise?

No      **IF NO, go to next page**  
 Yes

IF YES:

a. Type of noise you were exposed to:

b. Your age when exposed:  
  /  /     
years old

c. Which ear or side of your head was exposed?

- LEFT ear/side
- RIGHT ear/side
- BOTH ears/sides
- Not sure

Subject ID

*Do not fill in - for office use only*

### Non-Occupational/Recreation

/    /      
Month/Day/Year

Please tell us about any solvent or chemical exposures that you have had in your NON-Occupational/Recreation activities.

Copyright OHSU LENS-Q 2016 for rights and permissions contact [name] at [[contact]](mailto:[contact])  
Do not duplicate or distribute without written permission from [name]

## APPENDIX F: Questionnaire 3: Tinnitus Functional Index (TFI)

### TINNITUS FUNCTIONAL INDEX

Today's Date \_\_\_\_\_ Your Name \_\_\_\_\_  
*Month / Day / Year* \_\_\_\_\_ *Please Print* \_\_\_\_\_

Please read each question below carefully. To answer a question, select **ONE** of the numbers that is listed for that question, and draw a **CIRCLE** around it like this: **10%** or **1**.

#### I Over the PAST WEEK...

1. What percentage of your time awake were you consciously **AWARE OF** your tinnitus?

*Never aware ► 0 10% 20% 30% 40% 50% 60% 70% 80% 90% 100% ◀ Always aware*

2. How **STRONG** or **LOUD** was your tinnitus?

*Not at all strong or loud ► 0 1 2 3 4 5 6 7 8 9 10 ◀ Extremely strong or loud*

3. What percentage of your time awake were you **ANNOYED** by your tinnitus?

*None of the time ► 0% 10% 20% 30% 40% 50% 60% 70% 80% 90% 100% ◀ All of the time*

#### SC Over the PAST WEEK...

4. Did you feel **IN CONTROL** in regard to your tinnitus?

*Very much in control ► 0 1 2 3 4 5 6 7 8 9 10 ◀ Never in control*

5. How easy was it for you to **COPE** with your tinnitus?

*Very easy to cope ► 0 1 2 3 4 5 6 7 8 9 10 ◀ Impossible to cope*

6. How easy was it for you to **IGNORE** your tinnitus?

*Very easy to ignore ► 0 1 2 3 4 5 6 7 8 9 10 ◀ Impossible to ignore*

#### C Over the PAST WEEK...

7. Your ability to **CONCENTRATE**?

*Did not interfere ► 0 1 2 3 4 5 6 7 8 9 10 ◀ Completely interfered*

8. Your ability to **THINK CLEARLY**?

*Did not interfere ► 0 1 2 3 4 5 6 7 8 9 10 ◀ Completely interfered*

9. Your ability to **FOCUS ATTENTION** on other things besides your tinnitus?

*Did not interfere ► 0 1 2 3 4 5 6 7 8 9 10 ◀ Completely interfered*

#### SL Over the PAST WEEK...

10. How often did your tinnitus make it difficult to **FALL ASLEEP** or **STAY ASLEEP**?

*Never had difficulty ► 0 1 2 3 4 5 6 7 8 9 10 ◀ Always had difficulty*

11. How often did your tinnitus cause you difficulty in getting **AS MUCH SLEEP** as you needed?

*Never had difficulty ► 0 1 2 3 4 5 6 7 8 9 10 ◀ Always had difficulty*

12. How much of the time did your tinnitus keep you from **SLEEPING** as **DEEPLY** or as **PEACEFULLY** as you would have liked?

*None of the time ► 0 1 2 3 4 5 6 7 8 9 10 ◀ All of the time*

Please read each question below carefully. To answer a question, select ONE of the numbers that is listed for that question, and draw a CIRCLE around it like this: 10% or 1.
											
A	Over the PAST WEEK, how much has your tinnitus interfered with...	Did not interfere					Completely interfered				
		▼	0	1	2	3	4	5	6	7	8
13. Your ability to HEAR CLEARLY ? 0 1 2 3 4 5 6 7 8 9 10											
14. Your ability to UNDERSTAND PEOPLE who are talking? 0 1 2 3 4 5 6 7 8 9 10											
15. Your ability to FOLLOW CONVERSATIONS in a group or at meetings? 0 1 2 3 4 5 6 7 8 9 10											
R	Over the PAST WEEK, how much has your tinnitus interfered with...	Did not interfere					Completely interfered				
		▼	0	1	2	3	4	5	6	7	8
16. Your QUIET RESTING ACTIVITIES ? 0 1 2 3 4 5 6 7 8 9 10											
17. Your ability to RELAX ? 0 1 2 3 4 5 6 7 8 9 10											
18. Your ability to enjoy " PEACE AND QUIET "? 0 1 2 3 4 5 6 7 8 9 10											
Q	Over the PAST WEEK, how much has your tinnitus interfered with...	Did not interfere					Completely interfered				
		▼	0	1	2	3	4	5	6	7	8
19. Your enjoyment of SOCIAL ACTIVITIES ? 0 1 2 3 4 5 6 7 8 9 10											
20. Your ENJOYMENT OF LIFE ? 0 1 2 3 4 5 6 7 8 9 10											
21. Your RELATIONSHIPS with family, friends and other people? 0 1 2 3 4 5 6 7 8 9 10											
22. How often did your tinnitus cause you to have difficulty performing your WORK OR OTHER TASKS , such as home maintenance, school work, or caring for children or others?											
Never had difficulty ► 0 1 2 3 4 5 6 7 8 9 10 ◀ Always had difficulty											
E Over the PAST WEEK...											
23. How ANXIOUS or WORRIED has your tinnitus made you feel?											
Not at all anxious or ► 0 1 2 3 4 5 6 7 8 9 10 ◀ Extremely anxious or worried											
24. How BOTHERED or UPSET have you been because of your tinnitus?											
Not at all bothered or ► 0 1 2 3 4 5 6 7 8 9 10 ◀ Extremely bothered or upset											
25. How DEPRESSED were you because of your tinnitus?											
Not at all depressed ► 0 1 2 3 4 5 6 7 8 9 10 ◀ Extremely depressed											

Copyright Oregon Health & Science University

08.15.08

## APPENDIX G: Questionnaire 4: LENS-Q Adapted Survey for Stratification (High vs. Low Noise Exposure Group Stratification)

**LENS-Q Adapted for Police Officer Study:** By virtue of working in a career with required firearm use, all participants are automatically categorized as high noise. The point of this modified survey is to stratify participants into relatively higher and relatively lower exposure groups.

### Noise Exposure History Interview Questions

1. In your role as a police officer:
  - A. How often does your police officer job cause you to be exposed to loud noise(s) where you have to shout to be heard? (For example, loud equipment or trucks, loud ship or jet engines, exposure from the rifle range, sirens, K-9 noise, loud crowds, loud music (e.g. concert/band events), loud noise from construction sites)
    - a. Daily
    - b. Less than daily/more than weekly
    - c. Weekly
    - d. Less than weekly/more than monthly
    - e. Monthly
    - f. Less than monthly/more than yearly
    - g. Yearly
    - h. Less than yearly
    - i. Never
  
  - B. How likely are you to be wearing hearing protection when this occurs (circle one)?

Never	Rarely	Sometimes	Usually	Always
-------	--------	-----------	---------	--------
  
2. Have you served in the military? If yes:
  - A. How often did your military service cause you to be exposed to loud noise(s) where you had to shout to be heard? (For example, loud equipment or trucks, loud ship or jet engines, loud aircraft)
    - a. Daily
    - b. Less than daily/more than weekly
    - c. Weekly
    - d. Less than weekly/more than monthly
    - e. Monthly
    - f. Less than monthly/more than yearly
    - g. Yearly
    - h. Less than yearly
    - i. Never
  
  - B. How likely were you to be wearing hearing protection when this occurred (circle one)?

Never      Rarely      Sometimes      Usually      Always

C. How many years did you serve in the military? \_\_\_\_\_

3. In either your police officer position, your military service, or your recreational activities:

A. How often have you been exposed to sudden intense noise? (For example, shooting range, target practice, hunting, explosions, cannon fire, gun shot, music (e.g. drums), etc.)

- a. Daily
- b. Less than daily/more than weekly
- c. Weekly
- d. Less than weekly/more than monthly
- e. Monthly
- f. Less than monthly/more than yearly
- g. Yearly
- h. Less than yearly
- i. Never

B. Were you wearing hearing protection when this occurred (circle one)?

Never      Rarely      Sometimes      Usually      Always

4. A. How often did or do non-police officer/non-military jobs or recreational activities cause you to be exposed to loud noise(s) where you would have to shout to be heard?

- a. Daily
- b. Less than daily/more than weekly
- c. Weekly
- d. Less than weekly/more than monthly
- e. Monthly
- f. Less than monthly/more than yearly
- g. Yearly
- h. Less than yearly
- i. Never

B. Were you wearing hearing protection when this occurred?

Never      Rarely      Sometimes      Usually      Always

C. How many years did you work in a non-police officer/non-military job where you had to shout to be heard?

---

### **Noise Exposure Group Assignment Based on Interview Questions**

- Participants with a response to 1.A., 2.A., or 3.A. of monthly or more frequent exposure are assigned to the higher noise group. Participants with less than monthly exposure are assigned to the lower noise group.
- Participants with a response to 1.C., 2.C, or 4.C. of 5 years or more are assigned to the Higher Noise group.

## APPENDIX H: Questionnaire 5: 1-Minute Noise Screen (30-day post follow-up visit)

### 1-Minute Noise Screen

ID Number: \_\_\_\_\_ Date: \_\_\_\_\_

#### DURING THE PAST 30 DAYS,

1. How often were you around or did you shoot firearms such as rifles, pistols, shotguns, etc.?  
 Never    Less than weekly    Weekly    More than weekly    Daily
2. How often were you exposed to loud sounds while working on a paid job? By loud sounds, we mean sounds so loud that you had to shout or speak in a raised voice to be heard at arm's length.  
 Never    Less than weekly    Weekly    More than weekly    Daily
3. How often were you exposed to any other types of loud sounds, such as power tools, lawn equipment, or loud music? By loud sounds, we mean sounds so loud that you had to shout or speak in a raised voice to be heard at arm's length.  
 Never    Less than weekly    Weekly    More than weekly    Daily

Noise exposure score: \_\_\_\_\_

Post-op	Postoperative
Pre-op	Preoperative
PTS	Permanent Threshold Shift
SAE	Serious Adverse Event(s)
TTS	Temporary Threshold Shift
UA	University of Akron
WIN	Word in noise
WU	Washington University School of Medicine
ZNS	Zonisamide

1 PURPOSE

This document describes the planned statistical strategies for the analysis of data for the “Pharmaceutical Interventions for Noise-Induced Hearing Loss–Acute Exposure Treatment (PINIHL-AET)” Study. The document will be shared with the members of the Data Safety Monitoring Board (DSMB) and will be modified based on their feedback and requests.

Data reports will be prepared for the DSMB and will be part of the DSM report that will be prepared by the study team with assistance from the study statistician. The DSM report will be prepared for the DSMB semi-annually and at other times at the discretion of the DSMB. The DSM report will be reviewed by the DSMB, and will be submitted to the PI. The DSMB must meet at least every six months beginning six months after study activation at Washington University beginning six months after enrollment of the first patient at the secondary site, or due to Adverse Events (AE) or Serious Adverse Events (SAEs) to ensure subject safety through data, process or conduct of study and recommend to the sponsor on continuation, modification, or termination of the study, and no more than one month prior to the due date of the DSM report to the PI.

In the event of future amendments to the protocol, this SAP will be modified as necessary to account for changes relevant to the statistical analysis.

1.1 RESPONSIBILITIES

Pharm-Olam will perform the statistical analyses and is responsible for the production and quality control of all derived datasets and tables, listings, and figures.

2 INTRODUCTION

2.1 STUDY DESIGN

A randomized, double-blind, placebo-controlled clinical trial has been designed. Police officers identified with TTS will be randomized to receive either ZNS or a placebo.

Study subjects will be recruited from the Akron Police Department, Summit County Police Department, and other local surrounding police departments. Police officers will be offered participation if they are training for firearm certification as part of their standard occupational requirements. These are officers that would be recommended and/or required to complete these trainings/certifications despite this investigation and this investigation will have no influence on audiologic recommendations.

Interested police officers will then undergo screening for TTS following shooting range noise exposure. Those officers identified with TTS will be randomized via an interactive randomization tool (IRT) and assigned to a study group. Once assigned the subject will be provided a kit that will contain either ZNS (100 mg PO) or a placebo.

2.2 STUDY OBJECTIVES

2.2.1 Primary Objective

To determine if ZNS is more effective than placebo in preventing permanent threshold shift (PTS) in police officers identified with temporary threshold shift (TTS) following shooting range noise exposure.

2.2.2 Secondary Objectives

To determine if ZNS is more effective than placebo in the prevention of additional auditory dysfunction in police officers following shooting range noise exposure as measured by ultra-high frequency audiometry, distortion product otoacoustic emissions (DPOAE), electrocochleography (EcochG) and words-in-noise (WIN) scores, and to determine a PGx link between NIHL and ZNS treatment effect.

2.3 Study Population

This study is a randomized, controlled clinical trial with two parallel groups. Police officers identified with TTS following shooting range noise exposure will be randomized to receive either ZNS (100 mg PO) or a placebo. We plan to enroll approximately 132 subjects (police officers) with TTS over 4 years. Subjects will be randomized in a balanced fashion into one of the two arms: ZNS (100 mg PO) or Placebo.

2.4 Randomisation

Eligible subjects will be randomized via an interactive randomization tool (IRT) in a balanced fashion into the 2 study groups based on the randomization list generated from the study statistician using a computer algorithm written in SAS® using randomly selected blocks of sizes 2. Within each block of 2, there will be 1 subject assigned to each study group. To balance noise-exposure history across study arms we will employ stratified randomization. The subjects will be stratified based on noise exposure survey responses as described in table below, and will then be randomized to study groups. The random assignment of subjects to the different study groups will be associated with consecutively assigned study identification numbers (Study ID) which will be unique for each study participant. The stratified randomization kit list will be provided to Advanced Rx who will package and label the drug for shipment to the pharmacist for each participant. Each bottle will be labeled with the kit number, study ID, and instructions on how to take the study medication. The bottle will not contain any information of the treatment allocation.

Name	Description
1: High Noise	Screening: LENS-Q Adapted for Police Officer – 1A Or 2A Or 3A = a.Daily, Or b.Less than daily/more than weekly, Or c.Weekly, Or d.Less than weekly/more than monthly Or e.Monthly OR 1C Or 2C Or 4C \geq 5 Years
2: Low Noise	Screening: LENS-Q Adapted for Police Officer – 1A AND 2A AND 3A = f.Less than monthly/more than yearly, g.Yearly, h.Less than yearly Or i.Never OR 1C AND 2C AND 4C $<$ 5 Years

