## 5.2 Randomization

Following identification of TTS, eligible participants will be randomized via an interactive randomization tool (IRT) in a balanced fashion into one of two study groups: ZNS (100 mg PO) or placebo. Randomization will be based on a randomization list generated from the study statistician using a computer algorithm written in SAS using randomly selected blocks of sizes 2. Within each block of 2, there will be 1 subject assigned to each study group. To balance noise-exposure history across study arms we will employ stratified randomization. The subjects will be stratified based on noise exposure survey responses (see table below), and will then be randomized to study groups. The random assignment of subjects to the different study groups will be associated with consecutively assigned study identification numbers (Study ID) which will be unique for each study participant. The stratified randomization kit list will be provided to Advanced Rx who will package and label the drug for shipment to the pharmacist for each participant. Each bottle will be labeled with the kit number, study ID, and instructions on how to take the medication. The bottle will not contain any information of the treatment allocation.

- ZNS (100 mg PO) group
- Placebo PO group

Name	Description
1: High Noise	Screening: LENS-Q Adapted for Police Officer

Name	Description
	
1A Or 2A Or 3A =
 
a.Daily, Or b.Less than daily/more than weekly, Or c.Weekly, Or d.Less than weekly/more than monthly Or e.Monthly
 
OR
 
1C Or 2C Or 4C <math>\geq 5</math> Years

2: Low Noise	
Screening: LENS-Q Adapted for Police Officer
 
1A AND 2A AND 3A =
 
f.Less than monthly/more than yearly, g.Yearly, h.Less than yearly Or i.Never
 
OR
 
1C AND 2C AND 4C <math>< 5</math> Years

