## **8.0 REGULATORY AND REPORTING REQUIREMENTS**

The entities providing oversight of safety and compliance with the protocol require reporting as outlined below. Please refer to Appendix A for definitions and Appendix B for a grid of reporting timelines.

Adverse events will be tracked for the Akron site post dose within 30 minutes, 24 hours, and at 30 days. All adverse events must be recorded on the AE tracking case report form (CRF). AEs related to study medication only will be tracked.

Reporting requirements for Washington University study team may be found in Section 8.1. Reporting requirements for secondary site study teams participating in Washington University-coordinated research may be found in Section 8.2.

In the event of a Serious Adverse Event determined by the PI to necessitate the breaking of the blind, the intervention assignment will be revealed by the independent programmer to the medical staff doctor caring for the patient. In the event the statistician is unable to be reached in a timely manner, to assure the safety of the subject, the blind can be broken by [name] and information will be shared with the medical staff assuming care for the research subject.

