2.5 Treatment Assignment and Blinding

The study will be “masked” or “blinded” in the sense that all the study subjects and the study team members will be blinded to the assignment in the study groups. Only the pharmacist who will prepare the study drug kits and the unblinded statistician will have access to the kit assignments. The Medical Monitor will be contacted. A copy of the randomization list with study ID assignments will be saved in a limited access folder on a secure network server at Pharm-Olam. The Medical Monitor will be contacted in emergent medical cases when knowing the treatments assignment is mandatory for clinical care of the study subject.

The data will be presented without having the treatment assignments of individual study subjects made known to study team members including the study PI. Table shells will be blinded. If DSMB members find any safety issues, they may request specific unblinded data. Table shells for DSMB (content and formats) will be agreed upon prior to start of study.

Subjects will receive one time dose of oral ZNS or matching placebo after training if TTS is identified on audiogram 5-30 minutes after shooting. Subjects will be instructed to take study drug without food. We will recommend that capsules be swallowed whole per the current approved labeling.

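### With a fixed, printed block size of 2, revealing one officer's allocation also reveals that of the block partner

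*SAP*

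**What the plan says.** SAP 2.4 and Protocol 5.2 describe the list in almost the same words. It is generated "using randomly selected blocks of sizes 2", and "Within each block of 2, there will be 1 subject assigned to each study group". No other block size appears in either document. The reason given for stratifying is: "To balance noise-exposure history across study arms we will employ stratified randomization". There are two strata, High Noise and Low Noise, set by the adapted LENS-Q answers taken at screening. Allocations are tied to study IDs issued in consecutive order, and the label carries the ID: "Each bottle will be labeled with the kit number, study ID, and instructions on how to take the study medication". The arm is not on the label.

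On blinding, SAP 2.5 says that "all the study subjects and the study team members will be blinded to the assignment in the study groups". Only the pharmacist and the unblinded statistician hold the kit assignments. Individual unblinding is nevertheless foreseen by three routes:

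- the Medical Monitor, in emergencies where care depends on knowing the arm (Protocol 4.0, SAP 2.5);
- a serious adverse event, where "the intervention assignment will be revealed by the independent programmer to the medical staff doctor caring for the patient" (Protocol 8.0);
- the DSMB: "If DSMB members find any safety issues, they may request specific unblinded data" (SAP 2.5).

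Neither document keeps the block size from site staff. Neither says how the other member of a pair is protected once one member's blind is broken.

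**The concern.** A 1:1 block of 2 is the most transparent permuted block there is: the two members are always in opposite arms. Anyone who learns one member's arm, knows that the size is 2 and can place the pair in its stratum also knows the other member's arm. The protocol supplies the size. The consecutive IDs and the LENS-Q answers held at the site make the order in the stratum at least partly recoverable.

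Two things are exposed. The first is allocation concealment. Entry depends on a temporary shift of at least 10 dB on a behavioural audiogram at Visit 3, just before randomisation (Protocol 3.1b and 9.0). A person who already knew the next arm could be influenced in calling that result. The second is the blind at outcome. PTS is a shift of at least 10 dB at any frequency from 2 to 6 kHz in at least one ear (SAP 3.2), measured by a button-press audiogram (Protocol 5.1). Such a measure can respond to expectation in the officer or the tester.

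**Working it through.** The plan states no figure for predictability, so there is none to reproduce. Its power figure does not depend on block length. As a context check, exact one-sided Fisher power for 50% against 25% with 66 per group at 0.025 is 81.3%, against 80.5% stated.

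**Inputs.** Block size B = 2, one officer per arm in each block, two strata (SAP 2.4, Protocol 5.2). Planned total 132 (SAP 2.7). Interim at 22 per group (SAP 9, Protocol 12.4).

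**Formulas for a 1:1 permuted block of size B**

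- Chance that a given block-mate is in the opposite arm once one arm is revealed: (B/2)/(B − 1).
- Share of allocations forced by the earlier ones, if all earlier ones are known: 1/(B/2 + 1). Enumeration of all sequences confirms it.
- Correct-guess rate, if all earlier allocations are known: by enumeration.

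| B | Opposite arm, one revealed | Forced, all earlier known | Correct guess, all earlier known |
|---|---|---|---|
| 2 | 1/1 = 1.00 | 1/2 = 50% | 75.0% |
| 4 | 2/3 = 0.67 | 1/3 = 33% | 70.8% |
| 6 | 3/5 = 0.60 | 1/4 = 25% | 68.3% |

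For a random mix of 4 and 6, simulation gives a correct-guess rate of about 69%. For B = 2 the 50% is 132/2 = 66 officers if every block fills.

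**Which column applies.** The last two columns assume that every earlier allocation is known, as in an open-label trial. Here the capsules match and the blind normally holds, so the second column is the relevant one.

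**Officers exposed.** With u allocations revealed, blocks of 2 expose at most 2u officers. The documents give no expected u. As an assumed range, u = 1, 2 and 5 give at most 2/132 = 1.5%, 4/132 = 3.0% and 10/132 = 7.6%. With blocks of 4 or 6, a single revealed allocation fixes no other officer's arm.

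**A guess instead of a reveal.** If an officer is judged to be on ZNS with probability p, the partner is on placebo with the same probability p. The guess gains no certainty by being passed on.

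**Direction.** If the revealed officer was first in the pair, the partner is the next officer in the stratum. If second, it is the previous one. At the planned 34 officers a year (Protocol 12.4) the average gap between enrolments is 365/34 ≈ 11 days, so a reveal soon after dosing could precede the partner's entry. Training days may cluster officers more closely; the documents do not say.

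**Cost of blocks of 4 and 6.** The largest running imbalance in a stratum is B/2: 3 instead of 1, or 6 instead of 2 over two strata. At worst the final split is 69 to 63. The variance of the difference then rises by a factor of about 66²/(69 × 63) = 4356/4347 = 1.002. At the interim the worst split is 25 to 19, a factor of 22²/(25 × 19) = 484/475 = 1.019.

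**The case against.** The strongest case on the other side is that the safeguards work and that none of the unblinding routes leads to the person testing hearing. The arm goes to the treating doctor or to an independent DSMB, and SAP 2.5 keeps individual assignments from the study team, including the PI. Capsules are matched, the officer gives the response, and program code derives PTS status. This stands: no passage shows a revealed arm reaching a hearing tester. The partner must also be identified by stratum and order, and the documents do not say whether IDs run within each stratum or across both. An unpaired last officer in a stratum has no partner at all.

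Four stronger readings are tempting, and the documents do not support them:

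- That somnolence or dizziness at 24 hours gives away the partner's arm. The documents list such effects but give no rate by arm after the single dose, and a guess carries over only its own uncertainty.
- That it is always the next officer who is exposed. It may equally be the previous one.
- That half of all allocations are known in advance. That would need every earlier allocation to be known.
- That the wording on random selection contradicts itself. It can be read as a random choice between the two possible orders within a pair. It then describes a fixed block size clearly, though a reader could take it to mean varying sizes.

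What the objection does not remove is the certain link within a pair once one arm is really revealed. Both documents disclose it, and larger blocks would avoid it.

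**Conclusion.** The point holds as a cheap improvement to the design, not as an error in any stated figure. Given an actual unblinding, the block partner's arm is certain with blocks of 2, whereas for a given block-mate the probability is 0.67 with blocks of 4 and 0.60 with blocks of 6. The size is at most one additional officer per unblinding. The conclusion assumes that the observer knows the block size, which is printed, and can place the pair in the stratum sequence, which is feasible but not assured.

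It is a risk to the blind and to allocation concealment. The documents do not show that either has been breached, and sample size, power and alpha are untouched.

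**What to change.** For kits not yet issued, generate the list within each noise stratum with block sizes drawn at random from 4 and 6. Blocks of 2 should not be in the mix, because they would keep the certain link for some pairs. Switch at a pair boundary in each stratum. Delete the block size from Protocol 5.2 and SAP 2.4, say only that permuted blocks of varying size are used, and hold the sizes in the restricted randomisation file that SAP 2.5 already provides for.

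The cost is a new kit list, relabelling by the outside packager, an update of the randomisation tool, and an amendment to both texts. Arm sizes may differ by up to 3 per stratum (6 overall) instead of 1 (2 overall), with the small loss of precision shown above. The interim count of 22 per group should then be described as approximate.

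If the list cannot be reissued, the plan should at least say how the other member of a pair stays masked after an unblinding, for example by recording who learned the arm and keeping those persons away from the partner's hearing tests.

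### The Low Noise stratum is not the complement of High Noise, Appendix G settles only part of the overlap, and all three statements of the rule cite a survey item (1C) that is not on the form

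*SAP*

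**What the plan says.** SAP 2.4 and the table in Protocol 5.2 give the same stratification rule, in two parts for each stratum.

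- **High Noise.** The frequency part starts "1A Or 2A Or 3A = a.Daily" and runs down to monthly. The years part is joined to it by OR ("e.Monthly OR 1C Or 2C Or 4C" at least 5 years).
- **Low Noise.** The frequency part is "1A AND 2A AND 3A = f.Less than monthly/more than yearly" or any rarer category. The years part is again joined by OR: "i.Never OR 1C AND 2C AND 4C" under 5 years. In the Protocol table this OR stands on its own line above "1C AND 2C AND 4C", so it is not an artefact of text extraction.

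Appendix G of the Protocol states the rule in prose. Monthly or more on 1A, 2A or 3A means the higher group. Then: "Participants with less than monthly exposure are assigned to the lower noise group". A separate bullet sends 5 years or more on 1C, 2C or 4C to the higher group. No order of precedence is given.

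The adapted survey in Appendix G has items 1A-1B, 2A-2C, 3A-3B and 4A-4C. The last item under question 1 begins "B. How likely are you to be wearing hearing protection when this occurs (circle one", and question 2 follows directly. Question 2 is put only to officers with military service.

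**The concern.** A two-level stratification factor needs two definitions that exclude each other and together cover everyone. If High is A or B, Low has to be neither A nor B. Here Low is written as not A **or** not B, which overlaps with High.

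The missing item 1C is a separate defect. It does not create the overlap, but it leaves the years part undefined and changes how large the overlap is. The unscored military items add a further gap.

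The stratum is used in the IRT to balance noise history between arms. The supportive logistic model (SAP 7.1.1) and the secondary ANCOVA (SAP 7.1.2) adjust for noise history in a high/low split. Neither section cites the SAP 2.4 table, but no other split is defined, so the stratum rule is its likely source. Two programmers working independently, as SAP 11.2 requires, could code the same officer differently from the same text. The analysis value could also differ from the stratum the officer was randomised in.

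**Working it through.** **Inputs.** F = any of 1A, 2A, 3A monthly or more. Y = any years item at least 5. The rules are those of SAP 2.4, Protocol 5.2 and Appendix G. The plan gives no figure for the size of either stratum, so there is none to reproduce. The stated 80.5% power (66 per group, 50% against 25%, one-sided 0.025) is recovered by the Walters arcsine approximation for Fisher's test, and it uses no stratum information.

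**Step 1, logic.**

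- High = F or Y.
- Low as written = (not F) or (not Y).
- Both = High and Low = exactly one of F and Y true.

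| Officer | Table, missing 1C ignored or counted as under 5 | Table, missing 1C fails the years test | Appendix G |
|---|---|---|---|
| F and Y | High | High | Higher |
| F, not Y | **Both** | High | Higher |
| not F, Y | **Both** | **Both** | **Both** |
| not F, not Y | Low | Low | Lower |

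In the middle column the Low years part can never be true, so Low reduces to not F.

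**Step 2, answer patterns.** Treat each of the three frequency items and the two existing years items (2C, 4C) as yes/no. That gives 2^5 = 32 patterns. F is false in 1 of 8 frequency patterns and Y is false in 1 of 4 years patterns.

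- Missing 1C ignored: both = 7×1 + 1×3 = 10; High only = 7×3 = 21; Low only = 1.
- Missing 1C fails: both = 1×3 = 3; High only = 28; Low only = 1.

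**Step 3, share of officers.** The documents give no response distribution. Assume P(F) = 50-90%, P(Y) = 20-50%, and independence.

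- Table reading, F(1−Y) + (1−F)Y: highest at F = 0.9, Y = 0.2, where 0.72 + 0.02 = 0.74. Lowest is 0.50 (for example 0.45 + 0.05 at F = 0.9, Y = 0.5). So 50-74%, or about 66 to 98 of 132.
- Appendix G, or missing 1C fails, (1−F)Y: from 0.1×0.2 = 0.02 to 0.5×0.5 = 0.25. So 2-25%, or about 3 to 33 of 132.

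Wider assumptions (F 50-95%, Y 10-60%) give 41-86% and 0.5-30%.

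**Step 4, military items.** In the investigators' earlier sample (Protocol 1.5) 40% of 30 officers had served, which leaves 60% for whom 2A and 2C would not apply. If an unanswered 2A and 2C were treated as failing the Low conditions, an officer with no service, infrequent exposure and under 5 years would meet neither definition. If they are scored never and 0 years, that officer is Low. The documents do not say which applies.

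**Step 5, after correction.** With Low = (not F) and (not Y), using only items on the form, the 32 patterns split into 31 High, 1 Low, 0 both and 0 neither.

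**The case against.** The strongest reply is that this is a drafting slip with little effect. Appendix G, read with the tables, places every officer with monthly or more exposure in the higher group, which removes the larger of the two conflicting cells (0.72 of the 0.74 at the top of the range). Scoring no military service as never and 0 years is the natural convention, since 2A already offers a never option. The IRT must return one stratum for each officer and may already resolve ties to High. Allocation is 1:1 in blocks of 2 within whichever stratum is assigned. The primary test is an unstratified Fisher's exact test, and the logistic model is supportive.

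Most of this stands. It limits the size of the problem and keeps it away from the primary result. It does not remove the contradiction. Appendix G itself assigns infrequent, 5-or-more-years officers to both groups and also cites 1C. No text says that Appendix G overrides the tables, and the IRT specification is not in the documents.

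A reader might also infer that an officer without military service can never qualify as Low. The documents do not support that: what is missing is a coding convention.

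**Conclusion.** The rule is wrong as written in SAP 2.4 and Protocol 5.2, and it is incomplete in Appendix G. Item 1C is cited in all three places and is not on the survey. The infrequent, 5-or-more-years officers are in conflict on every reading of the years part considered here. The frequent, under-5-years officers are in conflict only on the tables, and only if missing items count as under 5 years.

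The ranges of 50-74% and 2-25% rest on assumed response rates and independence. They should be shown together, because which one applies depends on how 1C is handled.

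Three stronger readings are tempting and are not supported:

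- **That most officers are in fact in both strata.** There is no response distribution, and Appendix G settles the larger cell.
- **That the randomised comparison or the primary result is compromised.** The Fisher test, its alpha and its power do not use the stratum.
- **That the plan states the model covariate is this stratum.** The link is a reasonable inference and is not written down.

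The correction should be made, but the primary conclusion does not depend on it.

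**What to change.** 1. In SAP 2.4 and Protocol 5.2, define Low Noise as not High Noise: 1A, 2A and 3A all less than monthly **and** 2C and 4C both under 5 years.
2. State that military items are scored as never and 0 years for officers with no service.
3. Remove 1C from the rule, unless the IRT already takes it from a defined source; in that case, name the source. Substituting length of police service from the Case History form is not equivalent to deleting 1C. With a 5-year cut it would move every officer with 5 or more years' service to High.
4. Make Appendix G agree with the tables.
5. Check the IRT logic. If it already resolves ties to High, keep it and correct the text.
6. Before unblinding, state in SAP 7.1.1 and 7.1.2 that the noise covariate is the stratum the IRT assigned, and set its derivation to match.

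The cost is a short text correction in three places, a sentence in the SAP analysis sections and one check of the IRT specification. Sample size and power do not change.
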